3.3. Safety Variables

Safety endpoints include:

- Change from baseline to each scheduled assessment in BMD measured by DXA of lumbar spine (L1-L4), femoral neck, and total hip
- Incidence and severity of treatment emergent adverse events (TEAEs)
- Incidence and severity of hypoestrogenic TEAEs (hot flush)

CRS-BS-TP-000005 V 2.0

Page 20 of 99

- Time to the first post-treatment menses
- Changes in clinical laboratory assessments (hematology, biochemistry, coagulation parameters, hormones, lipids and urinalysis) from baseline to each scheduled assessment
- Any pathological changes from baseline in the endometrium as assessed by histology from endometrial biopsies
- Changes from baseline to each scheduled assessment in any other safety parameter including weight, vital signs, ECG, gynecological assessments and endometrial thickness

Safety analyses are described in Section 6.6.

3.4. **Exploratory Variables**

Exploratory endpoints include:

- Change from baseline in bone turnover markers at each scheduled assessment
- PK and PD of linzagolix

Exploratory analyses are detailed in Section 6.8 (and Section 6.4.3.33.for PK).

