5.5. Visit Windows

For all analyses except for the DXA assessments and the diary questionnaires, the visits as collected in the eCRF will be used.

The rules for visit day calculations are listed in Table 1 below.

E-diary questionnaires:

For diary questionnaires (EHP-30, EQ-5D-5L, HRPQ, HRUQ, PGIC, PPGIC, PGIS, PROMIS, SSIQ) except for the PSIQ, the e-diary dates of assessment of each visit will be checked versus the dates of same visit in eCRF to handle for e-diary visit errors. Only assessments within the window of the date of eCRF+/-14 days will be used in analyses. In case of multiple assessments falling within the same window of an eCRF date, the non-empty record with completion date closest to the eCRF date will be used.

Due to the war situation in Ukraine, some subjects from Ukraine sites may have completed visits and e-diary questionnaires but not collected the data in the eCRF. For all ediary questionnaires data of subjects from Ukraine sites with a later questionnaire date of 24FEB2022, the e-diary dates will be compared to theoretical visits dates instead of eCRF visits dates if eCRF dates are missing.

For data from discontinued visits, the discontinuation visit date should be compared to theoretical visit dates. Only assessments within the window of theoretical date +/-14 days will be used for analyses, if it is planned to have a such assessment at this visit and no other assessment is in the window. If a subject discontinued in the extension treatment period, date will be compared to the theoretical visit dates in the extension treatment period as described in Table 1. If a subject discontinued in the extension follow-up period, date will be compared to the theoretical number of the theoretical visit dates in the extension follow-up period, date will be compared to the theoretical number of the theoretical visit dates in the extension follow-up period, date will be compared to the theoretical number of the theoretical visit dates in the extension follow-up period, date will be compared to the theoretical visit dates in the extension follow-up period, date will be compared to the theoretical visit dates in the extension follow-up period, date will be compared to the theoretical visit dates in the extension follow-up period, date will be compared to the theoretical visit dates in extension follow-up period from Table 2.

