Note that assessments from discontinued visits in **Example** eDiary device are entered under Month 12 (Month 6 Extension FU in follow-up). They will be recoded as discontinued visits before applying the windowing rules.

Pharmacokinetics data

Visit windows rules for PK data will be the following:

- PK assessments will be included in analysis if:
 - Assessment is Pre-dose (or PK time = dose time), or IMP intake is not done on the day of PK sampling (i.e. considered as pre-dose), and,
 - PK assessment date is within +/-10 days of the theoretical visit and up to 2 days after last IMP intake for Month 12 visit.

If the PK sampling time is missing, or the IMP intake on the same day is done and the IMP intake time is missing then assessments will not be included.

IMP intake status (done/not done) and IMP intake time from the Pharmacokinetics eCRF page will be used.

PK samples analysed after the period of long term stability will be excluded.

DXA data

Visit windows rules for DXA assessments will be the following:

- The DXA assessment at Month 9 will be derived as the first non-missing DXA assessment with acceptable quality (accepted="Yes") and dated between Month 9 theoretical date (=Day 253) -28 days and Month 9 theoretical date + 28 days.
- The DXA assessment at Month 12 will be derived as the first non-missing DXA assessment with acceptable quality (accepted="Yes") and dated between Month 12 theoretical date (=Day 337 in the main study) -28 days and Month 12 theoretical date + 28 days.
- The DXA assessment at Month 6 Extension Follow-Up will be derived in the same way as the DXA assessment at Month 12. Theoretical date of Month 6 Extension Follow-up is 168 days after Month 12 theoretical date or after treatment discontinuation.

Other safety data:

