For other safety data, data from early discontinuation should be compared to theoretical visits dates. Only assessments within the window of theoretical date +/-14 days will be used for analyses, if it is planned to have a such assessment at this visit and no other assessment is in the window. If a subject discontinued in the extension treatment period, date will be compared to the theoretical visit dates in extension treatment period as described in Table 1. If a subject discontinued in the extension follow-up period, date will be compared to the theoretical visit dates in extension follow-up period, date will be compared to the theoretical visit dates in extension follow-up period, date will be compared to the theoretical visit dates in extension Follow-up period from Table 2.

For unscheduled safety assessments, if the assessment occurs within a window of theoretical date +/- 14 days for a planned eCRF visit for which it was planned per protocol to have such assessment, and no assessment was done for that visit, the assessment will be assigned to that visit. If the assessment is equally distant from two eCRF visits with no corresponding safety assessment, the assessment will be assigned to the next visit.

For biopsy, DXA assessment or laboratory assessment, if an assessment has been assigned in external data to a follow-up visit of the main study for subjects who entered in the extension study, the visit of assessment should be reassigned with the same rules described above for unscheduled safety assessment.

Visit	Theoretical Date
Month 6	Day 169
Month 7	Day 197

Table 1 Theoretical Visit Dates in Extension Treatment Period

CRS-BS-TP-000005 V 2.0

Page 29 of 99

Kissei / Cytel Confidential: This is a controlled document and shall not be changed, saved, copied or reproduced by any unauthorized person.

Month 8	Day 225
Month 9	Day 253
Month 10	Day 281
Month 11	Day 309
Month 12	Day 337

Table 2 Theoretical Visit Dates in Extension Follow-up Period

Visit	Theoretical Date
Month 1 ExFU	Month 12 or treatment discontinuation date + 28
Month 3 ExFU	Month 12 date or treatment discontinuation date + 84
Month 6 ExFU	Month 12 date or treatment discontinuation date + 168

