For serum levels of E2, P4, SHBG and LH, only the actual values at each time point will be summarized. Note: in the event of repeated values, the last non-missing value per study day/time will be used.

In addition, for E2, the proportion of subjects with the following categories:

- E2 <20 pg/mL,
- E2 between \geq 20 and <60 pg/mL,
- E2 ≥60 pg/mL

at each visit and for each treatment group will be provided in tables and graphically (bar charts).

For E2, samples analysed after the period of long-term stability should be excluded from analysis.

The relationship between E2 serum levels and bone mineral density loss will be explored graphically in different ways:

• First, the E2 serum level measured at Month 12 will be plotted on the x-axis against the percent BMD change from baseline measured at Month 12 on the left side y-axis and the percentage of subjects with clinically meaningful reduction of DYS (resp. NMPP) with stable or decreased use of analgesics for EAP on the right side y-axis. Thresholds from the Month 3 Meaningful Change Threshold analysis will be used for DYS and NMPP. A second plot showing the BMD percent change from baseline 2 (for subjects who are in placebo arm in the main study) and reduction of DYS and NMPP from baseline 2 will be produced.

- Second, bar charts will be produced at each visit from Month 6 to Month 12 and presented with the percent BMD change from baseline to Month 12 on the y-axis and the proportion of subjects with the E2 categories described above on the x-axis. Similar graphs will be produced for each of the BMD sites (femoral neck, hip, and spine), and for the BMD percent change from baseline 2 (for subjects who are in placebo arm in the main study).
- Lastly, bar charts of the proportion of subjects with the E2 categories described above on the x-axis will be plotted against the percentage of responders according to the primary endpoint, using DYS and NMPP thresholds from the Month 3 Meaningful Change Threshold analysis. Bar charts with percentage of responders from baseline 2 will be shown as well.

For P4, since P4 above 10 nMol/L may suggest luteal activity and hence ovulation, the proportion of subjects with P4 >10.0 nMol/L at least once from Month 6 to Month 12 will also be provided in tables.

The number and percentage of subjects with cholesterol values in the following categories

• LDL ≥ 160 mg/dL

Cute CONFIDENTIAL - Kissei

- LDL ≥ 190 mg/dL
- HDL < 40 mg/dL

will be reported at each visit.

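### Estradiol, LH and progesterone at treatment-period visits have no limit on time since last dose, so a few off-drug samples can enter the tables and especially the progesterone count

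*SAP*

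**What the plan says.** For hormones, SAP 6.6.3 states: "For serum levels of E2, P4, SHBG and LH, only the actual values at each time point will be summarized". It names two filters, neither about dosing. One is "For E2, samples analysed after the period of long-term stability should be excluded from analysis"; the other leaves local-laboratory results out of the summaries.

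SAP 3.3 counts hormones among the safety laboratory variables ("Changes in clinical laboratory assessments (hematology, biochemistry, coagulation parameters, hormones, lipids and urinalysis) from baseline to each scheduled assessment"), so the general rules of SAP 5.5 apply:

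- Default: "For all analyses except for the DXA assessments and the diary questionnaires, the visits as collected in the eCRF will be used".
- Withdrawal visits: "For other safety data, data from early discontinuation should be compared to theoretical visits dates". Then "Only assessments within the window of theoretical date +/-14 days will be used for analyses", provided that such an assessment is planned at that visit and the window holds no other one.
- Unscheduled samples go to a planned visit within 14 days that has no sample of its own.

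Theoretical dates run from Day 1 of the main study, not from the last dose.

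PK has its own condition in SAP 5.5: "PK assessment date is within +/-10 days of the theoretical visit and up to 2 days after last IMP intake for Month 12 visit". Protocol 10.7.2 asks women who stop early for the Month 12 procedures, which include E2, LH, P4 and SHBG (Protocol 10.2.1.5). It waives only the PK sample when no IMP was taken the day before.

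The hormone values feed the visit tables, the E2 bands (below 20, 20 to below 60, and 60 pg/mL or more), the count of women with P4 above 10 nmol/L at least once from Month 6 to Month 12, the E2-responder charts, and a figure in which "the E2 serum level measured at Month 12 will be plotted on the x-axis against the percent BMD change".

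**The concern.** E2, LH and P4 show how far the drug suppresses the ovarian axis. A value taken after dosing has stopped no longer answers that question, yet it would appear in a treatment-period row with nothing to mark it. The plan sees the problem for PK, with a 2-day limit and a withdrawal waiver, but carries neither over to the hormones drawn at the same visit.

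The P4 count is the most exposed output, because one late sample is enough to classify a woman as showing possible ovulation. The E2-responder charts carry a mismatch. Response is measured up to and including the last treatment day (SAP 6.4.2.1), while the E2 value beside it may come from after that day.

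**Working it through.** The documents give no figure for this point, so there is none to reproduce. The check follows the assignment rule and then bounds the number of samples.

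**1. Which days can be assigned.** Theoretical visits fall on Days 169, 197, 225, 253, 281, 309 and 337 (SAP 5.5, Table 1), 28 days apart. Windows of 14 days either side meet: 169 + 14 = 183 = 197 - 14. The last ends at 337 + 14 = 351. None of Days 170-351 is uncovered, so calendar day alone never excludes an E2, LH or P4 withdrawal sample in that span.

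**2. Two cases, both with Month 8 attended on Day 225.**
- Withdrawal visit on Day 235: 235 - 225 = 10 days, inside the Month 8 window, which already has a sample. Not used.
- Last dose Day 232, withdrawal visit Day 242: 242 - 225 = 17 days, outside Month 8; 253 - 242 = 11 days, inside Month 9. Used as a Month 9 value, 10 days off drug.

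For a woman attending on schedule, samples in roughly the first 14 days after her last visit are dropped and those in the next 14 are carried forward. If withdrawals are evenly spread (assumption), about half are used.

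**3. Drug remaining.** Half-life is 15-20 h (Protocol 5.5.1). Fraction left = 2^(-hours/half-life):

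| Days since dose | 15 h | 20 h |
|---|---|---|
| 1 | 33% | 44% |
| 2 | 11% | 19% |
| 3 | 3.6% | 8.2% |
| 7 | 0.04% | 0.30% |
| 10 | 0.0015% | 0.024% |

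A completer takes her last dose the day before Month 12 (Protocol 10.2.1), so she is at the 1-day row.

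**4. How many samples.** Planned entry is 450 x 0.80 x 0.80 = 288 (Protocol 13.2). With equal retention (assumption), that is 288/3 = 96 per main-study arm and 96/2 = 48 per placebo-switch group. Suppose 5-20% withdraw, evenly over six visits (assumption):
- Switch group: 48 x 0.05/6 = 0.4 to 48 x 0.20/6 = 1.6 per visit.
- Continuing arm: 96 x 0.05/6 = 0.8 to 96 x 0.20/6 = 3.2 per visit.

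Halving for step 2 gives about 0.2-0.8 and 0.4-1.6. Women still dosing at withdrawal reduce these further.

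**5. Effect on the 75 mg groups.** Let p be the on-drug share with E2 below 20 pg/mL, and c the off-drug share of a visit's samples, none below 20. The reported share falls by p x c. With p = 30-70% (assumption) and c from 0.05/6 = 0.8% to 0.20/6 = 3.3%, the fall is 0.30 x 0.83% = 0.2 points to 0.70 x 3.3% = 2.3 points, before halving.

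**6. Effect on the P4 count.** This accumulates over visits, so there is no division by six. If a fraction q = 10-50% of withdrawal samples exceed 10 nmol/L (assumption), the count rises by at most 0.05 x 0.10 = 0.5 points to 0.20 x 0.50 = 10 points, before halving.

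**7. E2 against BMD.** Month 12 BMD needs a DXA within 28 days of Day 337, that is Days 309-365 (SAP 5.5). Women who stop before Month 9 have no withdrawal DXA (Protocol 10.7.2). The Month 12 hormone window is Days 323-351. Exposure is therefore mainly through withdrawals near Months 11-12 and delayed Month 12 visits.

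**The case against.** The strongest reply is that few samples are involved and nothing confirmatory depends on them. The study tests no hypotheses, the hormone outputs are descriptive, all laboratory data are listed, and the last-dose date is derived (SAP 5.2.1). Early discontinuers also have a Month 1 follow-up visit due 28 days, give or take 7, after the last intake (Protocol 10.2.2.1), so withdrawal visits would normally fall before long gaps build up. All of this stands and limits the size. It does not close the gap: a stated rule still labels off-drug values as treatment-period values. The Extension PD Set does not help either, because it removes subjects for major deviations, not samples by time off drug, and SAP 6.6 runs the laboratory summaries on the safety set.

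Several stronger readings are tempting and do not hold:

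- *Every withdrawal sample is used.* It is not. The visit must have no other sample.
- *A visit row in a switch group could shift by several percentage points.* That needs about three recovered samples at one visit among 48, roughly twice the top of the range in step 4.
- *The E2 figures support the choice of dose.* SAP 6.6.3 describes a graphical exploration and no more.
- *PK at Months 7-11 has the same hole.* Those samples must be pre-dose, or taken with no intake that day, and within 10 days of the visit. The withdrawal waiver removes the requirement for most off-drug ones.
- *Off-drug samples always raise E2.* In the 200 mg groups the add-back estradiol stops too, so E2 may move either way.

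**Conclusion.** The concern holds in limited form. As written, SAP 5.5 and 6.6.3 allow off-drug E2, LH and P4 values into the treatment-period tables, the E2 categories, the E2-responder charts and the P4 count, through withdrawal visits, unscheduled samples and delayed Month 12 visits. The P4 count is the most exposed. The E2-BMD plots are exposed little. The co-primary endpoints are untouched.

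The size rests on assumed withdrawal of 5-20%, evenly spread, and on equal retention across arms; the documents give none of these. Nor do they give a hormone recovery time. The half-life shows when the drug is gone, not when the ovary recovers, so the estimates in steps 5 and 6 are upper bounds. The E2 distortion is upward for 75 mg alone and uncertain for 200 mg with ABT. The point is worth correcting because a stated rule misclassifies values and the remedy is simple.

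**What to change.** Add to SAP 5.5 or 6.6.3: E2, LH and P4 are included in treatment-period summaries, the P4 count and the E2 figures only if sampled no more than 2 days after the last IMP intake. List the excluded samples with days since last dose.

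The 2-day limit is the SAP's own Month 12 PK rule. It is a convention borrowed for hormones, not derived from a recovery time, and on-schedule completers at about 1 day are unaffected.

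The cost is one sentence and a date filter on data already collected (the last-dose date and daily eDiary intake). A few samples move from tables to listings, including any from a woman still on treatment who had missed more than 2 days.

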10.2.1.1 Study visit: Month 6 (Day 169 \pm 3 days)

After all Month 6 assessments pertaining to the main study have been made and the subject has been confirmed to be eligible to proceed in the extension study (see section 9.2), the subject will be requested to sign the extension-specific ICF that she was given at the Month 5 visit.

Note: inclusion in the extension study will not be postponed if the results of any Month 6 assessment are not available on the day of Month 6 visit. Subjects will be required to stop the treatment if the results obtained after enrollment meet the discontinuation criteria defined in Section 10.7.2.1.

After signature of the extension-specific ICF, the subject will be dispensed new treatment kits. The subject will take her daily dose of study medication at the study site from these newly dispensed kits. The exact time of dosing (hour/minute) will be recorded in eCRF.

In addition, the subject will:

- receive contraception counselling and will be given double barrier contraception (condoms with spermicide), if requested, to be used until 3 months after treatment end. If the subject is at risk for

acquiring HIV, she must be reminded to use double non-hormonal barrier contraception without spermicides (eg: condoms and diaphragms).

- be provided/prescribed a limited quantity (as per Investigator's judgement) of standard doses of permitted analgesics as rescue medication for EAP for the duration of the study.
- receive calcium 500 to 1000 mg and vitamin D 400 IU supplementation

Upon completion of the visit, the subject will be provided with emergency contact phone numbers and will be scheduled for her next visits.

10.2.1.2 Study visits: Month 7 (Day 197 -3/+2 days) and Month 8 (Day 225 ± 3 days)

The following tests and evaluations will be performed :

- eDiary completion compliance check
- ePRO and ClinRO completion, ideally before any other procedures or assessments:
 - at Month 7 visit: EHP-30, EQ-5D-5L, PROMIS, mPGIS, PGIC, HRUQ, HRPQ with mPGIS and PGIC completed last
 - at Month 8 visit: mPGIS, PGIC, HRUQ and HRPQ with mPGIS and PGIC completed last.
- Concomitant treatments recording
- AE recording
- Completion of the paper C-SSRS questionnaire (version for "already enrolled subjects" (see Appendix S) for patients responding to the C-SSRS for the first time during the study, or version "since last study visit" (see Appendix T) for patients for whom the C-SSRS was completed at the previous study visit)

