10.5 LINZAGOLIX AND KP017 PLASMA LEVELS

PK blood samples will be collected from each subject at each study visit during the Treatment Period for determining linzagolix and KP017 plasma levels.

At the visits where IMP intake is at site, i.e. at Months 6, 7, 8, 9, 10 and 11 visits, PK sampling will be performed before IMP intake. The approximate time of dose administration on the four previous days and time of PK sampling will be recorded in the eCRF.

In case of early discontinuation visit, PK sampling is not required at the withdrawal visit if the subject had no IMP administration the day prior to the withdrawal visit.

Details of the blood sampling process, sample handling and shipment are described separately in a laboratory manual provided by the central laboratory.

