Appendix A. Schedule of study assessments – Treatment Period

Schedule of study assessments – Treatment Period							
Timing ¹	Treatment Period						
	M6 ²	M7	M8	M9	M10	M11	M12
Informed Consent	X						
Inclusion-Exclusion criteria	X						
Physical examination (including weight)	X			X			X
Columbia-Suicide Severity Rating Scale	X	X	X	X	X	X	X
ECG ³	X	X	X	X	X	X	X
Vital signs	X	X	X	X	X	X	X
Urine pregnancy test	X	X	X	X	X	X	X
Endometrium TVUS	X			X			X
Gynecological examination	X			X			X
Endometrial biopsy	X ⁴						X ⁴
Manual breast examination	X						X
Clinical laboratory & urinary protein dipstick	X ⁵	X	X	X ⁵	X	X	X ⁵
BMD by DXA	X			X ⁶			X
Adverse events	X	X	X	X	X	X	X
Concomitant medication	X	X	X	X	X	X	X
Contraceptive dispensing and counselling	X	X	X	X	X	X	X
Permitted analgesic prescribing/dispensing	X	X	X	X	X	X	X
Vitamin D and calcium dispensing	X	X	X	X	X	X	X
Subject eDiary completion check	X	X	X	X	X	X	X

¹ All visits should take place at the end of the defined period (i.e. M7 visit should be scheduled at the end of Month 7, M8 visit should be scheduled at the end of Month 8, etc.). All visit dates should be calculated from the date of Day 1 visit (in the main study). A month is defined as 28 days/4 weeks. Visits should be scheduled ± 3 days (-3/+ 2 days for Month 7 visit) from the calculated date.

² All Month 6 assessments except informed consent and inclusion/exclusion criteria would have been performed as part of the main study (18-OBE2109-003 - Edelweiss 3).

³ ECG should be performed at about the same time but before the PK sample

⁴ If endometrium thickness in TVUS is ≤ 5 mm, no endometrial biopsy will be necessary.

⁵ Overnight fasting is required.

⁶ Only for subjects who met the following criterion at any site on the M6 DXA scan: $-2.5 < Z\text{-score} \leq -1.5$

Schedule of study assessments – Treatment Period (cont'd)

Schedule of study assessments – Treatment Period							
Timing ¹	Treatment Period						
	M6 ²	M7	M8	M9	M10	M11	M12
IMP accountability	X	X	X	X	X	X	X
Dispense linzagolix/placebo kit	X	X	X	X	X	X	
Dispense ABT/placebo kit	X			X			
EHP-30, EQ-5D-5L and PROMIS ³	X	X		X			X
mPGIS, PGIC, HRUQ and HRPQ ³	X	X	X	X	X	X	X
SSIQ and PSIQ ³	X						X
Blood sample for PK ⁴	X	X	X	X	X	X	X
E2, LH, P4	X	X	X	X	X	X	X
SHBG	X			X			X
Bone biomarkers	X			X			X

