Mean pelvic pain scores for DYS and for NMPP will be calculated by averaging over the corresponding 28 calendar days immediately prior to and including the last treatment administration day. DYS will use days with uterine bleeding, defined as those days on which the subject records any uterine bleeding or spotting in the subject eDiary; NMPP will use days with no uterine bleeding. If a subject's mean score for DYS is undefined numerically because her daily eDiary reports indicate that she did not experience uterine bleeding on any days during the 28 calendar day period, then the mean score for DYS will be set equal to zero (which reflects the absence of any DYS during that reporting time period). Similarly, if a subject's diary reports indicate that she only experienced days with uterine bleeding during the period, then the mean score for NMPP will be set equal to zero. For subjects who discontinue treatment prior to Month 12 the last available observations prior to discontinuation will be used, in order to estimate the treatment effect while under treatment, that is the 28 calendar days immediately prior to and including the last dose date. The baseline mean overall pelvic pain scores for DYS and NMPP will be calculated by averaging over the two baseline menstrual cycles (as defined in section 6.2.2), which may not be exactly 28 days each. For both DYS and NMPP, responses of "None," "Mild," "Moderate," and "Severe" will be assigned a score of 0, 1, 2, and 3, respectively.

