6.6.3. Laboratory Data

Clinical laboratory values will be expressed using conventional SI units.

Hematology, coagulation parameters, chemistry and lipids were assessed at screening and at each visit during the extension treatment period (from M7 to M12), as well as at the M1 ExtFU and M3 ExtFU visits.

E2, progesterone (P4) and LH were assessed at each visit during the extension treatment period (from M6 to M12), as well as at M1 ExtFU and M3 ExtFU visits.

Serum levels of sex hormone-binding globulin (SHBG) were assessed on Month 6, Month 9 and Month 12 visits.

Blood samples were to be analyzed by the central laboratory. Due to the covid-19 situation, some samples may be collected by local laboratories.

For Hematology, coagulation parameters, chemistry and lipids, the actual value, change from baseline and change from baseline 2 (only for the subjects who are in the placebo arm in the

```
CRS-BS-TP-000005 V 2.0
```

main study) will be summarized for each visit for each treatment group. In the event of repeated values, the last non-missing value per study day/time will be used.

Semi-quantitative laboratory results will be imputed as follows: "<X.X" will be imputed as "X.X/2" and ">X.X" will be imputed as "X.X".

Evaluation of shifts for changes from baseline and for changes from baseline 2 (only for the subjects who are in the placebo arm in the main study) to all visits according to the normal ranges with categories "Low", "Normal", "High" where available (for ALT, AST, ALP, Bilirubin, Albumin, Calcium, Creatine Kinase) and according to normal/abnormal/abnormal clinically significant information collected otherwise, will be provided.

For Liver Function Test (LFT) parameters (ALT, AST, ALP, total bilirubin, albumin), evaluation of shifts for changes from baseline will be extended by the worst (highest) on-treatment value (including unscheduled assessments) according to the normal ranges with categories "Low", "Normal", "High" will be provided.

For the lipid panel (Triglycerides, HDL, LDL, Total Cholesterol, LDL/HDL ratio), the percent change from baseline and the percent change from baseline 2 (only for the subjects who are in the placebo arm in the main study) to each on-study visit will also be summarized.

Assessments from local laboratories will not be included in summaries and shift tables, as normal ranges may not be comparable.

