6.6.8.4. Columbia-Suicide Severity Rating Scale (C-SSRS)

The C-SSRS questionnaire prospectively assess the occurrence of treatment-emergent suicidal ideation and behavior.

Subjects completed:

- either the "Baseline" C-SSRS version, capturing lifetime history of suicidal ideation and behavior, for subjects who were still in screening period in the main study,

- or the "already enrolled subjects" C-SSRS version, for subjects already enrolled in the main or in the Extension study, and who were providing answers to the C-SSRS for the first time during the study

- the "since last study visit" C-SSRS version, dedicated to subjects for whom the C-SSRS was completed at the previous study visit, for use at all remaining study visits.

The "Baseline" C-SSRS version was to be completed during Screening, or at Day 1 if not done during Screening.

The number of subjects experiencing the following, at baseline and at any time post-baseline in the extension study, will be summarized for each month from Day 1 to Month 12 and from Month 6 up to Month 12. For Month 6 to Month 12 period, the "since study start" questions from already enrolled questionnaire will not be included, as it cannot be identify whether the event occurred between Day 1 and Month 6 or Month 6 and Month 12.

- Any suicidal ideation or behavior
 - Wish to be dead.
 - Non-specific active suicidal thoughts.
 - Active suicidal ideation with any methods (not plan) without intent to act.
 - Active suicidal ideation with some intent to act, without specific plan.
 - Active suicidal ideation with specific plan and intent.
- Any Suicidal Behavior
 - Actual attempt.

Page 71 of 99

CRS-BS-TP-000005 V 2.0

- Interrupted attempt.
- Aborted attempt.
- Preparatory acts or behavior.
- Completed suicide (Actual attempt leading to death) (not at baseline)
- Emergence of suicidal ideation.
- Worsening of suicidal ideation.
- Emergence of suicidal behavior.

Any suicidal ideation or behavior is defined as an answer "Yes" for at least one of five questions for suicidal ideation or for at least one of five questions for suicidal behavior.

Emergence of suicidal ideation/behavior is defined as having no suicidal ideation/behavior at baseline and having reported any type of suicidal ideation/behavior at any time post-baseline (including "Since Study Start" answers).

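### In the two placebo-switch groups, the Month 6 to Month 12 count of P4 above 10 nmol/L includes a sample taken before the first linzagolix dose

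*SAP*

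**What the plan says.** **P4.** SAP section 6.6.3 treats P4 above 10 nmol/L as a possible sign of luteal activity and plans that "the proportion of subjects with P4 >10.0 nMol/L at least once from Month 6 to Month 12 will also be provided in tables". The same section fixes the visits: "E2, progesterone (P4) and LH were assessed at each visit during the extension treatment period (from M6 to M12". For haematology, coagulation, chemistry and lipids it starts one visit later: "at each visit during the extension treatment period (from M7 to M12".

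**Order of events at Month 6.** Protocol section 10.2.1.1 places extension consent, kit dispensing and the first dose from the new kits later in the visit: "After all Month 6 assessments pertaining to the main study have been made and the subject has been confirmed to be eligible". The footnote to Protocol Appendix A agrees: "All Month 6 assessments except informed consent and inclusion/exclusion criteria would have been performed as part of the main study". Protocol section 10.5 also puts the Month 6 PK blood draw before dosing, which is indirect support because it concerns PK and not P4.

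**Baseline 2.** SAP section 6.2.2 defines a second baseline, for main-study placebo subjects only, as the last assessment before the first active dose in the extension.

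**Diary window.** For subjects who stop early, the co-primary section (SAP 6.4.2.1) uses the last available observations, "that is the 28 calendar days immediately prior to and including the last dose date". SAP section 6.4.3, on the secondary diary endpoints, allows fewer days if treatment stops less than 4 weeks after the first dose date. It does not say which first dose.

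**The concern.** A woman who switches from placebo has not taken linzagolix when her Month 6 P4 sample is drawn. If that one sample is above 10 nmol/L, the at-least-once rule classes her as positive for the extension period, whatever her six later samples show. By the SAP's own definition the value is a baseline, yet it is counted as an outcome.

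The continuing groups were already on the same drug at Month 6, so their Month 6 sample is a legitimate on-drug value. The four columns of the table therefore do not measure the same thing. The switch columns could suggest weaker ovulation suppression for a reason unrelated to the drug.

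The co-primary diary window has a smaller fault of the same kind. A switcher who stops within the first four weeks of the extension has days from before her first linzagolix dose averaged into her Month 12 result.

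**Working it through.** **Step 1: group size.** Protocol section 13.2 gives 450 randomised, 80% completing and 80% of those entering. 450 × 0.80 = 360 and 360 × 0.80 = 288, which reproduces the plan's figure. Assuming equal retention across the three main-study arms, 288 / 3 = 96 entrants come from placebo. At 1:1 that is 48 per switch group.

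**Step 2: the P4 proportion.** Let p be the share of a switch group with P4 above 10 nmol/L at Month 6 on placebo, and q the chance of a positive sample at each on-drug visit. The documents give neither, so both are assumed, and visits are treated as independent.

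- On-drug visits only (Month 7 to Month 12, six samples): 1 − (1 − q)^6
- As the SAP is written (Month 6 to Month 12): 1 − (1 − p)(1 − q)^6
- Excess: p(1 − q)^6

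| p | q | Month 7–12 | Month 6–12 | Women of 48, Month 7–12 → Month 6–12 |
|---|---|---|---|---|
| 10% | 0 | 0% | 10.0% | 0 → 4.8 |
| 30% | 0 | 0% | 30.0% | 0 → 14.4 |
| 50% | 0 | 0% | 50.0% | 0 → 24.0 |
| 10% | 2% | 11.4% | 20.3% | 5.5 → 9.7 |
| 30% | 2% | 11.4% | 38.0% | 5.5 → 18.2 |
| 50% | 2% | 11.4% | 55.7% | 5.5 → 26.7 |

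The q = 0 rows need no independence assumption. They show the floor: the printed proportion is never below p.

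**Step 3: comparison with the continuing groups.** Those groups have seven on-drug samples. With the same q = 2%, their proportion is 1 − 0.98^7 = 13.2%. A switch group with p = 30% would show 38.0% although linzagolix acts identically in both.

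**Step 4: diary window in the co-primary section.** Take extension day 1 as the Month 6 visit, consistent with SAP section 5.2.1, which assigns Month 6 diary data to the extension. If the last dose is on day d, the 28-day window holds 28 − d days from before the extension.

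| Last dose on extension day | Days before the extension | Share of window |
|---|---|---|
| 7 | 21 | 75% |
| 14 | 14 | 50% |
| 21 | 7 | 25% |
| 28 or later | 0 | 0% |

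Only last doses on days 1 to 27 are affected. If the window were cut at the first extension dose, a woman whose last dose is before day 12 could not reach the 12 completed diary days that SAP section 6.4.2.1.1 already requires.

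**The case against.** **The P4 values stay visible.** SAP section 6.6.3 summarises actual P4 values at each time point and lists all laboratory data, and the columns are labelled placebo followed by linzagolix. This stands in part. However, the by-visit summary does not give the share above 10 nmol/L, so a reader of the tables cannot remove the Month 6 positives, and the label does not say that a placebo sample is counted.

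**The size is assumed.** This stands. A reader might infer a firm, large inflation by taking the luteal share of a cycle as p. The documents contain no such rate, and that step would also assume that every woman on placebo ovulates. Only the direction and the floor follow from the plan.

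**The diary point is mostly handled.** This also stands, and a reader might wrongly extend the fault to every diary endpoint. Every entrant has completed six months in the main study, so the shorter-window clause in SAP 6.4.3 can have effect only if it refers to the first extension dose. Section 6.4.3 also requires a second summary that leaves out subjects who have already discontinued, and the 12-day minimum exists. Women who met discontinuation criteria at Month 6 are outside the Treatment Extension Analysis Set. What remains is the co-primary section, where no such clause is written. SAP section 6.4 says that endpoints are derived as in the main study, whose SAP is not available here and might contain a truncation rule.

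**Suicidality.** The C-SSRS counts "will be summarized for each month from Day 1 to Month 12 and from Month 6 up to Month 12". A form is scheduled at Month 6, and its since-last-visit version looks back before the extension. A reader might infer that suicidality on placebo is attributed to linzagolix. The documents do not support that. SAP section 6.6.8.4 drops the since-study-start answers because they cannot be placed before or after Month 6, so it defines the period by when the event occurred. Whether the Month 6 form is counted is an ambiguity and not a stated inclusion.

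**Conclusion.** The P4 point holds on the SAP's own visit list and baseline definition. In the two switch groups the at-least-once proportion has a floor of p that has nothing to do with linzagolix. If p lies between 10% and 50%, that is about 5 to 24 of 48 women per group when the on-drug rate is zero. These counts rest on 288 entrants, equal retention across arms and an assumed p. The continuing groups do not have this fault, so the comparison between columns is distorted.

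The co-primary diary window is a lesser point. It affects only switchers whose last dose falls on extension days 1 to 27. Few are to be expected, and the number is not given.

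No group that carries the primary objective is affected. Protocol section 13.5 makes the switch groups a secondary objective and section 13.1 plans no hypothesis test. The matter should be corrected because, with no test, the tabulated percentages are themselves the result. It does not threaten the study's main conclusion.

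**What to change.** 1. **SAP 6.6.3.** For main-study placebo subjects, count P4 above 10 nmol/L only from samples after the first extension dose (Month 7 to Month 12), and show the Month 6 proportion separately as Baseline 2. If the four columns are to be compared, use the Month 7 start in all of them, so that each has six on-drug samples.
2. **SAP 6.4.2.1.** Repeat the shorter-window clause of section 6.4.3 and, in both places, key it to the first extension dose for main-study placebo subjects. Apply the existing 12-day minimum to the days that remain.
3. **SAP 6.6.8.4.** Add one sentence saying whether the Month 6 since-last-visit form belongs to the Month 6 to Month 12 period. The section's own reasoning points to leaving it out.

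The cost is SAP wording and a date condition in the affected programs. No new data are needed. A few switchers who stop very early would lose a diary value.
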